## NON-INTERVENTIONAL (NI) STUDY PROTOCOL

### PASS Information

Title	An Active Surveillance, Post-Authorization Safety Study (PASS) of Serious Infection, Malignancy, Cardiovascular (CV) and Other Safety Events of Interest among Patients Treated with Tofacitinib for Moderately to Severely Active Rheumatoid Arthritis (RA) within the Swedish, Population-based, Anti-Rheumatic Treatment in Sweden (ARTIS) register
Protocol Number	A3921314
Protocol Version Identifier	v 3.0
Date	February 14, 2022
EU Post Authorisation Study (PAS) Register Number	EUPAS31157
Active Substance	L04AA29 Tofacitinib
Medicinal Product	Xeljanz® (tofacitinib)
Product Reference	EU/1/17/1178/001-004
Procedure Number	EMA/H/C/0004214
Marketing Authorisation Holder (MAH)	Pfizer Europe
Joint PASS	No
Research Question and Objectives	Research Question: What are the rates of safety events special interest in RA patients treated with tofacitinib and among RA patients treated with other advanced targeted therapies?  Objectives:

090177e199570500\Approved\Approved On: 13-Feb-2022 20:25 (GMT)

090177e199570500\Approved\Approved On: 13-Feb-2022 20:25 (GMT)

	
To estimate the rates of serious infections, malignancy (overall, excluding NMSC), subtypes of lymphoma, lung cancer, CV events, MACE, MI, VTE (DVT and PE) and other safety events of interest, including fractures, among patients with RA in Sweden who initiate tofacitinib. Rates will also be estimated among 1) patients with RA who have not been treated with biologic or targeted synthetic disease modifying antirheumatic drugs (DMARDs), 2) patients with RA who initiate biologic DMARDs (bDMARDs) and 3) the general population to provide context for rates observed on tofacitinib. Further, event rates will be estimated in elderly patients aged 65 years and older.
 
Pending feasibility, rates of malignancy (overall, excluding NMSC), subtypes of lymphoma, lung cancer, serious infection, CV events, MACE, MI, VTE and other event rates, including fractures, will be compared between tofacitinib treated RA patients and other comparator cohorts using using multivariable Cox regressions adjusting for sex, age, year of treatment start, treatment history, disease severity, comorbidities and other potential confounders for more refined evaluation of safety concerns.

Country(-ies) of Study	Sweden

## 2. LIST OF ABBREVIATIONS

Abbreviation	Definition
ACR	American College of Rheumatology
ADR	adverse drug reaction
AE	adverse event
ARTIS	Anti-Rheumatic Treatment in Sweden
BID	bis in die (twice daily)
AS	ankylosing spondylitis
bDMARD	biologic disease modifying antirheumatic drug
CABG	coronary artery bypass graft
CI	confidence interval
CLL	chronic lymphocytic leukemia
COPD	chronic obstructive pulmonary disease
CRP	c-reactive protein
csDMARD	conventional synthetic disease modifying antirheumatic drug
CV	cardiovascular
CVD	cardiovascular disease
DAS 28	disease activity score 28
DMARD	disease modifying antirheumatic drug
DVT	deep vein thrombosis
EC	European Commission
EMA	European Medicines Agency
EPITT	European Pharmacovigilance Issues Tracking Tool
ESR	erythrocyte sedimentation rate
EU	European Union
EULAR	European League Against Rheumatism
GEP	Good Epidemiological Practice
GI	Gastrointestinal
GPP	Guidelines for Good Pharmacoepidemiology Practices
HAQ	health assessment questionnaire
HR	hazard ratio
Hx	history
HZ	herpes zoster
IBD	inflammatory bowel disease
ICD	International Classification of Diseases
ICD10	International Classification of Diseases version 10
ICH	International Council on Harmonisation of Technical Requirements for Registration of Pharmaceuticals for Human Use
IEA	International Epidemiological Association
IEC	independent ethics committee
IQR	interquartile range
ISPE	International Society for Pharmacoepidemiology
IL	Interleukin
IR	incident rate
IRB	institutional review board
JA	juvenile arthritis
JAK	janus kinase
LTE	long term extension
MI	myocardial infarction
MACE	major adverse cardiovascular event
MTX	methotrexate

090177e199570500\Approved\Approved On: 13-Feb-2022 20:25 (GMT)

Abbreviation	Definition
NDA	New Drug Application
NHL	non-Hodgkin lymphoma
NI	non-interventional
NMSC	non-melanoma skin cancer
NSAIDs	non-steroidal anti-inflammatory drugs
OI	opportunistic infection
OT	other rheumatic disease
PA	polyarthritis
PAS	post-authorization study
PASS	Post-Authorization Safety Study
PCI	percutaneous coronary intervention
PE	pulmonary embolism
PML	progressive multifocal leukoencephalopathy
PPV	positive predictive value
PsA	psoriatic arthritis
PY	person-years
RA	rheumatoid arthritis
RMP	risk management plan
SAP	statistical analysis plan
SAS	Statistical Analysis Software
SIR	standardized incidence rate
SJC	swollen joint count
SmPC	Summary of Product Characteristics
SpA	spondyloarthropathies
SRQ	Swedish Rheumatology Quality Register
Std	standardized
TB	tuberculosis
TJC	tender joint count
TNFi	tumor necrosis factor inhibitor
tsDMARD	targeted synthetic disease modifying antirheumatic drug
VAS	visual analog scale
VTE	venous thromboembolism
Yrs	years

#### 4. ABSTRACT

**Title:** An Active Surveillance, Post-Authorization Safety Study (PASS) of Serious Infection, Malignancy, Cardiovascular (CV) and Other Safety Events of Interest among Patients Treated with Tofacitinib for Moderately to Severely Active Rheumatoid Arthritis (RA) within the Swedish, Population-based, Anti-Rheumatic Treatment in Sweden (ARTIS) register.

**Version:** Final Protocol (V3.0)

**Date:** 14 February 2022

**Rationale and Background:** Tofacitinib is a potent, selective inhibitor of the Janus kinase (JAK) family of kinases with a high degree of selectivity relative to other kinases in the human genome. Tofacitinib was approved in the European Union (EU) in March 2017 at a dose of 5 milligrams (mg) administered twice daily (BID) for the treatment of adult patients with moderately to severely active RA who have responded inadequately to, or who are intolerant to, one or more disease-modifying antirheumatic drugs (DMARDs). To enable assessment of safety events of special interest including rare events and endpoints with long latency periods, Pfizer will implement a post-approval, active surveillance study of tofacitinib-exposed patients using actively collected prospective data included in the ARTIS register.

**Research Question:** What are the rates of safety events of special interest in RA patients treated with tofacitinib and among RA patients treated with other advanced targeted therapies?

**Objectives:** To estimate the rates of serious infections, malignancy (overall, excluding NMSC), subtypes of lymphoma, lung cancer, CV events, major adverse cardiovascular events (MACE), myocardial infarction (MI), venous thromboembolism (VTE; deep venous thrombosis [DVT] and pulmonary embolism [PE]) and other safety events of interest, including fractures, among patients with RA in Sweden who initiate tofacitinib. Rates will also be estimated among RA patients who initiate biologic DMARDs (bDMARDs), bDMARD and targeted synthetic DMARD (tsDMARD) naïve RA patients, and the general population to provide context for tofacitinib rates. Pending feasibility, a comparative analysis is planned as a secondary objective. Pending feasibility, rates of malignancy (overall, excluding NMSC), subtypes of lymphoma, lung cancer, serious infection, CV events, MACE, MI, VTE, and other event rates, including fracture, will be compared between tofacitinib-treated RA patients and the comparator cohort using methods that adjust for sex, age, year of treatment start, treatment history, disease severity, comorbidities, and other potential confounders. In response to the June 2021 signal evaluation procedure, subtypes of lymphoma, lung cancer, and MACE have been added as study endpoints (MI and lymphoma (overall) were already included as a study endpoints). Further, rates of events, including serious infections, MACE, MI, VTE and malignancies excluding NMSC, will be estimated in elderly patients aged 65 years and older.

**Study Design:** This active surveillance study will use existing data from the existing ARTIS register, an ongoing, prospective, observational, disease-based cohort started in 1999 with the primary aim of studying the safety of new therapies for RA during routine post-marketed clinical use.

**Population:** The study population will comprise all patients with RA enrolled within the ARTIS register who receive tofacitinib following EU approval and marketing, through the end of the study period. Three comparator cohorts will be assembled for risk characterization purposes: (1) RA patients who are treated with bDMARD (2) RA patients who are naïve to bDMARDs and tsDMARDs, and (3) a general population cohort.

**Variables:** The study variables include baseline patient characteristics (ie, clinical and demographic characteristics, comorbidities and current and past therapies) and safety events of interest including, but are not restricted to, the following: serious infections, malignancies (including lymphoma subtypes and lung cancer), CV events (including MACE), and VTE (DVT and PE).

**Data Sources:** Core baseline and follow up data, including patient demographics, disease characteristics, and treatment will be based on data from the ARTIS register, the Swedish Patient Register, and Swedish Rheumatology Quality Register (SRQ). ARTIS data will be augmented with linkages to the Swedish Patient, Prescribed Drug, Cancer, Medical Birth, Contagious Disease, Total Population, and Causes of Death Registers.

**Study Size:** This is a descriptive study without pre-specified hypotheses. All eligible patients in the Swedish registers will be included, with no upper limit on the sample size. The feasibility of more refined comparative analyses to evaluate safety concerns that adequately adjust for patient channeling and confounders will be assessed at an interim time point and after 7 years will be based on statistical power.

**Data Analysis:** The initial analyses will consist of descriptive comparisons of baseline status and crude event rates between the different cohorts. The final analysis of endpoints will provide the rates of events overall and in subgroups defined by baseline characteristics. Pending feasibility, rates of malignancy (overall, excluding NMSC), lymphoma (overall and by subtype), lung cancer, serious infection, CV events, VTE, and other event rates will be compared between tofacitinib-treated RA patients and the comparator cohorts using methods that adjust for sex, age, year of treatment start, treatment history, disease severity, comorbidities, and other potential confounders. For lymphoma, incidence rates will be stratified by lymphoma subtypes; not limited to but including non-Hodgkin lymphoma (NHL), Hodgkin lymphoma, chronic lymphatic leukemia. Similarly, CV (e.g. myocardial infarction (MI), MACE, serious congestive heart failure) and VTE (DVT and PE) event rates will be stratified by type of event. Further, for the outcomes of MI and MACE, incidence rates of the safety events of interest will be stratified by patients with  $\geq 1$  CV risk factors versus no CV risk factors. Similarly, for the outcome of VTE, incidence rates of the safety events of interest will be stratified by patients with  $\geq 1$  VTE risk factors versus no VTE risk factors.

**Milestones:** Interim reports will be provided at 2, 4, 6 years after the start of data collection. A final report, including linked data, will include 7 years of data after start of data collection.

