### Objectives:

To estimate the rates of serious infections, malignancy (overall, excluding NMSC), lung cancer, subtypes of lymphoma, CV events MACE and MI, VTE (DVT and PE) and other safety events of interest, including fractures, among patients with RA in Sweden who initiate tofacitinib. Rates will also be estimated among 1) patients with RA who have not been treated with bDMARD or tsDMARD, 2) patients with RA who initiate bDMARDs, and 3) the general population to provide context for rates observed on tofacitinib. Pending feasibility, rates of malignancy (overall, excluding NMSC), lung cancer, subtypes of lymphoma, serious infection, CV events, MACE MI, VTE, and other event rates, including fractures, will be compared between tofacitinib-treated RA patients and other comparator cohorts using multivariable Cox regressions adjusting for sex, age, year of treatment start, treatment history, disease severity, comorbidities and other potential confounders for more refined evaluation of safety concerns. In response to the June 2021 signal evaluation procedure, subtypes of lymphoma, lung cancer, and MACE have been added as study endpoints (MI and lymphoma (overall) were already included as a study endpoints). Further, rates of events, including serious infections, MACE, MI, VTE, and malignancies excluding NMSC, will be estimated in elderly patients aged 65 years and older.

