#### **9.2.1.3. ts/bDMARD-naïve RA Cohort**

- At least two separate visits documented in Swedish Patient Register listing RA as a diagnosis code for the visit, with at least one visit at a unit of Rheumatology or Internal Medicine.
- Patients are censored from this cohort when they start tofacitinib or a bDMARD, but are eligible for subsequent inclusion into the respective drug-based cohorts defined above.
- To ensure a contemporaneous cohort, diagnosis of RA must have occurred after 01 January 2012.

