 The potential mechanism for increased PML risk is poorly understood. PML will be evaluated using both on drug and once-exposed always at risk approaches.

The primary analysis will assume a once exposed always at risk paradigm, as is frequently used in study of malignancy risk due to bDMARDs. Under this approach, follow up for each cohort continues from the cohort index date until the first of a malignancy event, loss to follow up, death or end of study. Follow up for each exposure cohort continues after switching to a new drug or discontinuation of treatment. This approach maximizes follow up time and the ability to capture long latency events, ie, events that occur or are detected years after exposure. Under this approach, events will be double-counted if a patient indexed to bDMARD switches to tofacitinib and a malignancy occurs subsequent to tofacitinib exposure. That is, the event will be assigned to both the bDMARD and the tofacitinib exposure cohorts as will the corresponding person years since index to the respective cohorts. Because tofacitinib is expected to be used as a later line therapy, switching is expected to be non-random with most tofacitinib patients having been included in the bDMARD cohort prior to initiation of tofacitinib. In such cases, the bDMARD rate will have more associated person-years and thus a relatively lower rate than the corresponding rate in the tofacitinib cohort.

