Status at entry	Exposed Tofacitinib	Third biologic		Second biologic		Comparator Cohorts First biologic			
		TNFi	Non-TNFi	TNFi	Non-TNFi	TNFi	Non-TNFi	Biologics-naive	General population
Total days spent in hosp (median, IQR)									
Reason for discontinuing previous biologic									
Safety, of those with information (%)									
Inefficacy, of those with information (%)									
Other, of those with information (%)									
Missing, of total (%)									

COPD=Chronic obstructive pulmonary disease; DAS: Disease activity scale; DMARD=disease modifying antirheumatic drug; HAQ= health assessment questionnaire; Hx=history IQR=interquartile range; MI=myocardial infarction; N=count; NSAID = non-steroidal anti-inflammatory drug; RA=Rheumatoid Arthritis; TNFi=tumor necrosis factor inhibitor.

090177e199570500\Approved\Approved On: 13-Feb-2022 20:25 (GMT)

Table II. Total number of events, crude and standardized incidence rates							
Outcome	Cohort	Patients	Events	Person-Years	IR	Std IR	Mean follow-up, yrs
For each event of interest							
	Tofacitinib						
	0 previous biologics						
	1 previous biologics						
	2 previous biologics						
	3+ previous biologics						
	Third bio starters, TNFi						
	Third bio starters, non-TNFi						
	Second bio starters, TNFi						
	Second bio starters, non-TNFi						
	First bio starters, TNFi						
	First bio starters, non-TNFi						
	Bonaïve RA Patients						
	General Population						
Notes: IR, Incidence Rate, RA=rheumatoid arthritis; Std IR standardised incidence rate to the age/sex distribution in the tofacitinib cohort; TNFi=tumor necrosis factor inhibitor; yrs=years.							

090177e199570500\Approved\Approved On: 13-Feb-2022 20:25 (GMT)

090177e199570500\Approved\Approved On: 13-Feb-2022 20:25 (GMT)

Table III. Results from adjusted Cox regressions comparing tofacitinib initiators to comparator cohorts for each outcome									
Outcome	Tofacitinib initiators vs.	HRa	95% CI	HRb	95% CI	HRc	95% CI	HRd	95% CI

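### As Table III is laid out, a hazard ratio of all tofacitinib initiators against ts/bDMARD-naive RA would mix the drug with prior biologic failure, because no listed model contains number of previous biologics

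*Protocol*

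**What the plan says.** The comparison is conditional. The Abstract (section 4, Objectives) states: "Pending feasibility, a comparative analysis is planned as a secondary objective". Under Data Analysis, rates are to be "compared between tofacitinib-treated RA patients and the comparator cohorts using methods that adjust for sex, age, year of treatment start, treatment history", followed by disease severity, comorbidities and other confounders. Section 8 repeats this and names the model: rates are to be "compared between tofacitinib-treated RA patients and other comparator cohorts using multivariable Cox regressions adjusting for sex, age, year of treatment start, treatment history". The title page and section 9.7.2 also list treatment history among the Cox adjusters.

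The Abstract (Population) lists three comparator cohorts; the second is "RA patients who are naïve to bDMARDs and tsDMARDs". Section 9.2.1.3 adds: "Patients are censored from this cohort when they start tofacitinib or a bDMARD". Section 9.3.2 expects tofacitinib to be a later-line drug, "with most tofacitinib patients having been included in the bDMARD cohort prior to initiation of tofacitinib".

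In Appendix 2, Table III is headed "Results from adjusted Cox regressions comparing tofacitinib initiators to comparator cohorts for each outcome". Its notes give four models:
- HRa: stratified by start year, adjusted for age and sex.
- HRb: HRa plus inpatient days and history of infection, cancer, MI, diabetes, COPD and joint replacement.
- HRc: HRb plus rheumatoid factor, HAQ, disease duration, DAS28, DMARDs and steroids.
- HRd: HRc with HAQ and DAS28 in quartiles and a missing indicator.

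Table IV stratifies by number of previous biologics, but only against bDMARDs. Section 9.7.2 says the reports will contain tables in line with these shells.

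**The concern.** Number of previous biologics is a baseline row in Table I and a stratifier in Tables II and IV, so the protocol treats it as important. It is absent from every Table III model. The term DMARDs in HRc most naturally means the concomitant-DMARD row of Table I, which is separate from the row for previous biologics.

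Against bDMARD starters this omission can be repaired by adjustment or by Table IV. Against the naive cohort it cannot be repaired for the biologic-experienced majority, because no naive patient has a comparable history. Section 9.9 itself says tofacitinib patients may have had multiple failed therapies and carry risk-raising comorbidities. A hazard ratio above 1 against naive RA could then be taken for harm from the drug, or a real excess could be discounted as background.

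**Working it through.** The protocol gives no figure for this contrast, so there is nothing to reproduce. The check has three steps.

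**1. Who can be compared.** Cross-classify by cohort and previous bDMARD or tsDMARD use. Naive with history: empty by definition. Naive without history: the whole cohort. Tofacitinib with history: most patients (section 9.3.2, no percentage given). Tofacitinib without history: the remainder. Only the two cells without history overlap. This concerns biologics and tsDMARDs only; naive patients may have csDMARD or steroid history.

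**2. Without a term for previous biologics (HRa to HRd).** Let f be the share of tofacitinib person-time in experienced patients, RR their event rate relative to naive RA, and the true drug hazard ratio 1. The tofacitinib rate is then the naive rate times (1 - f) + f x RR, so the expected hazard ratio is 1 - f + f x RR. Both f and RR are assumptions; the protocol gives neither.
- f = 0.6, RR = 1.2: 0.4 + 0.72 = 1.12.
- f = 0.9, RR = 1.5: 0.1 + 1.35 = 1.45.
- Wider range: f = 0.5, RR = 1.25 gives 0.5 + 0.625 = 1.125; f = 0.9, RR = 2 gives 0.1 + 1.8 = 1.90.

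No credit is given for inpatient days, comorbidity, HAQ, DAS28 or disease duration, which would absorb part of the difference in HRb to HRd.

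**3. With a categorical term for previous biologics.** That term fits the experienced tofacitinib cell exactly. The drug coefficient is then the ratio of bio-naive tofacitinib to naive RA, with expected value 1.00. For precision, take the 344 patients projected in section 9.5 for the first 24 months and 5 years each: 344 x 5 = 1,720 person-years, with later enrolment and losses ignored. Use 10 events per 1,000 person-years (the protocol's bDMARD malignancy rate, applied here to naive RA) and assume 30,000 naive person-years, or 300 events. Bio-naive tofacitinib events are 17.2 x (1 - f), and SE(log HR) = sqrt(1/events + 1/300).
- f = 0.5: 8.6 events, SE 0.35, 95% interval about 0.51 to 1.97.
- f = 0.7: 5.2 events, SE 0.44, about 0.42 to 2.39.
- f = 0.9: 1.7 events, SE 0.76, about 0.22 to 4.48.

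The expected count falls below the shell's minimum of 5 events once 17.2 x (1 - f) < 5, that is, f above about 0.71. Adding the term thus replaces the mixing with imprecision, and the estimate describes bio-naive initiators although the table labels it as all initiators.

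**The case against.** The strongest reply is that the protocol never commits to a hazard ratio against naive RA. Comparisons are secondary and depend on feasibility, which section 9.7.2 judges on power and on suitable overlap of populations. That section names only tofacitinib and bDMARDs for formal comparison, the power tables cover bDMARDs only, and section 9.2.1 includes the comparators for context. The Abstract's Objectives use the singular for the comparator cohort, and the Annex 2 checklist says no measure of association will be determined. Bio-naive status is already a Table II row, exposure cohorts are to be analysed by previous biologics use, Appendix 2 calls its shells a general outline, and final covariates go to the SAP.

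Much of this stands. A reader might infer that the plan promises this hazard ratio; it does not. A reader might also infer that adjusting for treatment history causes the mixing; it does not, since the mixing comes from leaving previous biologics out. Nor is the direction established for every outcome. Section 7.1 reports higher infection risk under TNF inhibitors than under DMARDs, but section 7.2 says initial large studies found no increased lymphoma risk in TNFi-treated patients.

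It does not dispose of the point. The title page, Abstract (Data Analysis) and section 8 speak of comparator cohorts in the plural, with naive RA among the cohorts named. Treatment history is an adjuster the protocol has already fixed, and the shell it tells reports to follow leaves out the biologic part of it. The strata in section 9.7.2 and Table II are described for rates, and Table IV excludes the naive cohort. An overlap criterion with no stated consequence does not say what happens to this contrast.

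**Conclusion.** The point holds as a conflict within the protocol. The text adjusts for treatment history; the Table III models omit number of previous biologics; and the document is unclear on whether naive RA is a formal comparator. If the shell were followed for that cohort, the hazard ratio could not separate tofacitinib from prior biologic failure.

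The size is illustrative: 1.12 to 1.45 with no drug effect if 60-90% of initiators are experienced and their rate is 1.2-1.5 times that of naive RA, before any credit for other covariates. The documents do not support reading these figures as a forecast, or as showing that a false harm signal will appear. The comparison may never be run, and the rate ratio will differ by outcome. The correction should be made before any comparative report.

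**What to change.** 1. In sections 4, 8 and 9.7.2, state which cohorts are formal comparators for adjusted hazard ratios and which serve as context only.
2. For the naive cohort, choose one of two routes. Either limit the adjusted hazard ratio to tofacitinib initiators with no previous bDMARD or tsDMARD and label the Table III row accordingly, or report only age- and sex-standardised rates marked as context. The row for 0 previous biologics in Table II is the starting point; as labelled it counts biologics only, so previous tsDMARD use must be excluded as well.
3. For the bDMARD comparison, include or stratify on number of previous biologics in the Table III models, so that they match the adjustment stated on the title page and in sections 4, 8 and 9.7.2.

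The cost is a sentence in each section and a relabelled table row. The drawback is few tofacitinib events in the bio-naive row: intervals will be wide, and some outcomes may miss the 5-event rule, in which case only rates are shown.

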## 6. MILESTONES

Milestone	Planned date
-----------	--------------

Registration in the EU PAS register	01 September 2019
Start of data collection	15 September 2019
Interim report	14 March 2021
Interim report	14 March 2023
Interim report	14 March 2025
End of data collection	14 September 2025
Final Study Report	14 August 2026

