#### 9.4.2. SRQ/ARTIS Linkage

Endpoint information also derives from the linkage of SRQ/ARTIS to nationwide Swedish health care registers. Compared to the ADR reports, the register linkage has many advantages in providing data on all comorbidities that have been diagnosed, unbiased by incomplete reporting from physicians or by subjective assessments on causality. Importantly, it also allows us to obtain data on comparator cohorts, so that any potential risk increases can be evaluated in light of risks among patients on other treatments, and the general Swedish population. The drawback is a lag time of between 1 and 2 years from when an event occurs until it can be analyzed and reported using the national health care registers. This delay is caused by the annual curation of the Patient and Cancer registers by the National Board of Health and Welfare (ie, data from each year is only made available after internal processing, usually 9 to 12 months later, and the processing of data requests.

090177e199570500\Approved\Approved On: 13-Feb-2022 20:25 (GMT)

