Certain patient characteristics which may influence VTE outcomes (e.g., smoking status, obesity and immobilisation), cannot be reliably captured, and thus may limit data interpretation. Inherited coagulation disorders encompass a broad range of conditions, and only a limited number of these can be reliably captured in the Swedish registers. While immobilisation cannot be captured in the Swedish registers, including inpatient care due to RA (i.e., RA as main diagnostic listing) will capture hospitalized patients who will be immobilized, and who will also be at a potentially higher risk for VTE (consensus guidelines recommend thromboprophylaxis for all admitted patients with inflammatory bowel disease (IBD) in the absence of contraindications). Additionally, some CV risk factors such as smoking status (as previously mentioned) and baseline total cholesterol/HDL ratio cannot be adequately captured within the Swedish registers, and thus will limit the assessment of the MACE and MI endpoints. For the outcome of lymphoma, the 3 main subtypes that can be adequately be captured in the Swedish registers are NHL, Hodgkin lymphoma and chronic lymphocytic leukemia (CLL). Other lymphoma subtypes that do not fit into these 3 main categories will not be captured in the study and thus may limit the assessment of this outcome.

This study will follow patients for a period of 7-years from therapy initiation. Conclusions may not be generalizable outside of the 7-year period since initiation of therapy.

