1.1 Does the protocol specify timelines for				
1.1.1 Start of data collection 				6
1.1.2 End of data collection 				6
1.1.3 Progress report(s)				
1.1.4 Interim report(s)				6
1.1.5 Registration in the EU PAS Register®				6
1.1.6 Final report of study results.				6

Comments:

Section 2: Research question	Yes	No	N/A	Section Number
2.1 Does the formulation of the research question and objectives clearly explain:				8
2.1.1 Why the study is conducted? (e.g. to address an important public health concern, a risk identified in the risk management plan, an emerging safety issue)				8
2.1.2 The objective(s) of the study?				8
2.1.3 The target population? (i.e. population or subgroup to whom the study results are intended to be generalised)				8
2.1.4 Which hypothesis(-es) is (are) to be tested?				8
2.1.5 If applicable, that there is no a priori hypothesis?				8

 Date from which information on the first study is first recorded in the study dataset or, in the case of secondary use of data, the date from which data extraction starts.

 Date from which the analytical dataset is completely available.

Comments:

--

Section 3: Study design	Yes	No	N/A	Section Number
3.1 Is the study design described? (e.g. cohort, case-control, cross-sectional, other design)				9.1

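### The Abstract's seven years after start of data collection contradict the Section 6 dates, and Section 9.9's seven years per patient cannot hold under open entry

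*Protocol*

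**What the plan says.** The Abstract (Section 4, Milestones) states: "Interim reports will be provided at 2, 4, 6 years after the start of data collection". It continues: "A final report, including linked data, will include 7 years of data after start of data collection". Section 6 gives the start of data collection as "15 September 2019", the end as "14 September 2025" and the final study report as "14 August 2026", with interim reports on 14 March 2021, 2023 and 2025.

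Section 9.4.2 warns of "a lag time of between 1 and 2 years from when an event occurs until it can be analyzed" for events taken from the national registers. Section 9.9 states: "This study will follow patients for a period of 7-years from therapy initiation". It then says that conclusions may not generalise beyond seven years after initiation.

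Four other places bear on how these are read:
- The Abstract (Population) and Section 9.2.1 let initiators enter from launch (product fully available April 2017) until the study period ends.
- Section 9.5 expects at least 5 years of follow-up, and only for those enrolled in the first 24 months.
- Section 12 describes the interim reports as reflecting 2, 4 and 6 years of the study period.
- The Annex 2 checklist footnotes define the start of data collection, for secondary data, as the start of extraction, and the end as "Date from which the analytical dataset is completely available".

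**The concern.** Two different claims share the number seven. One is a calendar window for the cohort, tied in the Abstract to the start of data collection. The other, in Section 9.9, is a length of follow-up for each patient. The first does not agree with the protocol's own dates. The second cannot be true of a cohort that admits new starters until the end.

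This matters most for lung cancer, lymphoma and overall malignancy. Section 9.3.2 makes the once-exposed-always-at-risk approach primary for these outcomes so that events arising years after exposure are captured, and Section 9.9 places the limit on conclusions at seven years after initiation. A reader who takes that limit at face value would think that an unremarkable malignancy rate speaks to years 0 to 7 after first exposure. Under the planned entry, person-time in the later years will be sparse or absent, so the statement errs in the reassuring direction.

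**Working it through.** **Inputs.** Section 6: start 15 Sep 2019, end 14 Sep 2025, final report 14 Aug 2026, interims 14 Mar 2021, 2023 and 2025. Section 9.4.2: lag 1 to 2 years. Section 9.2.1: launch April 2017 (day assumed to be the 1st). Section 9.5: constant accrual. Years are days divided by 365.25.

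**1. The Abstract's figures against Section 6.**
- Start to end of data collection: 6.00 years, not 7.
- Start to final report: 6.91 years. Seven years after the start is 15 Sep 2026, 32 days after the report is due, so the sentence fails even with no lag.
- Interims: 1.49, 3.49 and 5.49 years after the start, not 2, 4 and 6.

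**2. The same dates counted from launch.**
- Two, four and six years end on 1 April 2019, 2021 and 2023. Each interim report comes 1.95 years later, within the 1- to 2-year lag.
- Seven years end on 1 April 2024, which is 1.45 years before 14 Sep 2025 and also within the lag.

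So 2, 4, 6 and 7 years reproduce as cohort windows from launch, but not from the start of data collection.

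**3. Follow-up per patient.** Let T be the time from launch to the last date with linked events. With uniform entry over T and no attrition, mean potential follow-up is T/2 and the share reaching seven years is max(0, (T − 7)/T).

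| Lag counted back from | Lag (years) | T (years) | Mean (years) | Share reaching 7 years |
|---|---|---|---|---|
| End of data collection | 1 | 7.45 | 3.7 | 0.45/7.45 = 6% |
| End of data collection | 2 | 6.45 | 3.2 | 0% |
| Final report | 1 | 8.37 | 4.2 | 1.37/8.37 = 16% |
| Final report | 2 | 7.37 | 3.7 | 0.37/7.37 = 5% |

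For a window of exactly seven years from launch, the mean is 3.5 years, 2/7 = 29% reach five years, and only the very first starters reach seven.

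Part of this does not depend on the accrual pattern. Counted from the end of data collection, a 2-year lag leaves nobody with seven years, and a 1-year lag leaves only those who started before mid-September 2017. With no lag at all, anyone starting after mid-September 2018 still falls short (T = 8.45 years; 1.45/8.45 = 17% reach seven years under uniform entry).

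**4. Section 9.9 against Section 9.5.** Section 9.5 claims at least five years, and only for starters in the first 24 months. That matches a seven-year calendar window (24 months plus five years). It does not match seven years for each patient.

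**The case against.** The strongest reply is that September 2019 is the wrong origin. The checklist treats the start of data collection as the start of extraction, initiators are eligible from April 2017, and their earlier person-time counts. Read that way, the milestones and the lag do deliver a seven-year cohort window, and Section 12 speaks of the years of the study period that the interim reports reflect, not of when they are issued. This stands, and it rules out a stronger reading that a reader might infer: that the study observes only the 4 to 5 years left after subtracting the lag from the six years in Section 6. Those 4 to 5 years measure linked data after extraction began, not total observation.

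It can also be said that the lag in Section 9.4.2 runs to analysis and reporting, so taking all of it from the date the dataset becomes available may be too severe. That is fair, and the table therefore shows both anchors.

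Third, Section 7 speaks of tracking the cohorts over seven years, open entry is stated plainly, Appendix 2 Table II has a mean follow-up column for each outcome and cohort, and Section 9.3.2 leaves analyses of latency assumptions to the SAP. These points reduce the risk of misreading. They do not make the Section 9.9 sentence true, and a single mean does not show how much person-time lies in the later years since first exposure. Nor does the launch reading rescue the Abstract, which names the start of data collection as its origin.

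**Conclusion.** The point holds in two parts and is of moderate weight. First, the Abstract's seven-year and 2/4/6-year statements contradict Section 6 as written; they become consistent only with an origin at launch, which the Abstract does not give. Second, the per-patient statement in Section 9.9 fails for nearly all initiators when the lag is taken from September 2025, and for about five in six on the most generous lagged count from the final report date. The limit on conclusions that follows it therefore overstates the latency range covered per patient.

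The documents do not support saying that the cohort-level window is overstated. The follow-up figures rest on uniform accrual from 1 April 2017 to the data cut and on no attrition. Deaths and emigration would shorten follow-up, while earlier uptake would lengthen the mean. No endpoint definition, model or risk window changes; what changes is how far a reassuring malignancy result can be read.

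**What to change.** - **Abstract and Section 12:** state the origin of the years (first tofacitinib start, April 2017) and, for each interim report and the final report, the last date with complete linked data. Reconcile both with the dates in Section 6.
- **Section 9.9:** replace the promise of seven years from initiation with follow-up of up to the attainable maximum, and give the expected mean or median. Reword the limit on generalisability to match.
- **Malignancy results:** confine latency conclusions to the follow-up actually observed, supported by events and person-years by time since first exposure.

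The cohort-level references to seven years in Sections 7, 9.5 and 9.7.2 can stand once the origin is stated.

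The cost is protocol wording and one simple tabulation, with no new data. The stated per-patient follow-up will look less favourable.
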